## **MOBILE INTERACTION PERIOD:**

Participants will be asked to complete items in response to queries using mobile ecological momentary assessment (EMA); i.e., questions/questionnaires asked at a given time point outside of a laboratory setting via a mobile device. We will assess antecedent conditions prior to health risk behavior: smoking or binge eating among our smoking and binge eating samples, respectively. These antecedent conditions include mood, companionship, location, and temptation. We will offer the resources of Laddr? (a science-based behavior change intervention delivered via an interactive, self-directed mobile platform) to individuals and assess the effect of this mobile intervention system on putative targets of self-regulatory function. Laddr will also be used to deliver the EMAs to participants. Participants will use their own smartphones.

We will ask participants to respond to EMAs and to engage with the mobile intervention for 28 consecutive days. We will prompt them four times daily to inquire about health risk behavior and ask them to complete measures of self-regulation and potentially important contexts. Please see the attachment [EMA Questions] for the list of actual questions asked.

We will send the four prompts at random times within time windows (e.g., 8–

11:30 AM, 11:30 AM-3 PM, 3-6:30 PM, 6:30-10 PM). The time windows may vary based on participants' waking hours, and we will program through the software at least an hour between prompts (e.g., if a participant receives a prompt at 11 AM, he/she cannot receive another prompt until 12 PM). We will ask them to use Laddr daily to, at a minimum, update progress toward goals and complete various activities on the application that we expect will improve their self-regulation. Participants will be recommended priority therapy guides (binge eating for the binge eating sample; smoking for the smoking sample) and can also choose to engage with other guides, such as depression, anxiety, and substance use.

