Participants will also be asked to use devices that allow for objective measuring of behaviors of interest. We will ask participants in the smoking sample to provide carbon monoxide (CO) samples via a breath CO meter (iCO? Smokerlyzer?, Bedfont? Scientific Ltd.). The monitor measures breath CO in parts per million (ppm) based on the conversion of CO to CO2 over a catalytically active electrode. We will ask smoking participants to provide one CO sample in the same time window each day. Smoking participants will have a goal of smoking abstinence by the end of the study, as evidenced by a CO reading of less than 4 ppm. We will ask participants in the binge eating sample to wear a physical activity tracking device (Fitbit Flex 2?), which tracks

steps, distance, calories burned, active minutes, hourly activity, stationary time, and sleep.

Objective measures of eating are in a nascent phase, and all

participants in the binge eating sample are overweight or obese, making physical activity a suitable behavior to measure. We will ask binge eating participants to wear the activity tracker for at least 12 hours

per day. We will encourage participants to use a changing criterion design to set stepped goals, in which participants set a 7-day activity criterion goal and are encouraged to increase their criterion goals in each subsequent 7-day block if they achieve the goal on at least 4 of

	the 7 days. We will ask Binge eaters to also self-report their activity for the day in Laddr.
	Please see the attachments [Fitbit Flex 2] and [ICO Smokerlyser] for a description of each of the devices used in measuring our behaviors of interest.
	Participants in the smoking sample may use nicotine replacement medications, and we will track which participants use these medications. Potential participants taking medications for psychiatric reasons will be excluded from both samples.
	After completion of the 4-week mobile interaction period, participants will return for a 2.75 hour follow-up neuroimaging session, consisting of around 1.25 hour of practice, setup and assessments outside the scanner, and around 1.5 hours of scanning. Participants will be compensated in full at the completion of this session.
d.	Procedure Risks
	None of the proposed procedures involve more than minimal risk.
e.	Use of Deception in the Study
	Deception will not be used.
f.	Use of Audio and Video Recordings

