## 8. **PARTICIPANT POPULATION**

## a. Planned Enrollment

We plan to recruit a local sample of 100 subjects; because of attrition, we may need to recruit up to 125-154 individuals in order to obtain 100 complete subjects. Sample will consist of 50 smokers and 50 individuals who binge eat (BED). These are two exemplar populations that putatively involve self-regulatory dysfunction.

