Applying Novel Technologies and Methods to Inform the Ontology of Self-Regulation: Aim 4

Statistical Analysis Plan

NCT03687658

August 29, 2023

Statistical Analysis Plan (SAP)

Objective: The primary objective of the analyses is to assess changes across time in various measures in binge eaters and smokers. Specifically, we aim to determine if there is a significant effect of time (day 1 to 28 of EMA responses) on each of the outcome measures.

1. Data Management:

Raw data will be cleaned and any inconsistencies will be resolved. Any missing data will be identified and excluded.

2. Descriptive Statistics:

Generate summary statistics (mean, standard deviation, frequency, and percentages) for all outcomes of interest, stratified by day.

3.Outcome Measures:

a. Binge eaters: a23 (Loss of Control over Eating)
Question: When you ate most recently, did you lose control over your eating?
Yes (Score: 1)
No (Score: 0)

b. Binge eaters: a22 (Overeating)
Question: Since the last prompt, when you ate most recently, did you overeat?
Yes (Score: 1)
No (Score: 0)

c. Smokers: a15 (Cigarette Consumption) Question: Since the last prompt, how many cigarettes have you smoked?

4. Statistical Analysis Methods:

For a23 (Loss of Control over Eating) and a22 (Overeating): A generalized linear mixed model (GLMM) with a binomial distribution using a logit link function will be employed. This will account for the repeated measures design, where participants provide multiple responses over days. Primary Predictor: Day (representing days 1 through 28 of EMA collected responses). Random Effect: Participant ID (id).

For a15 (Cigarette Consumption): A generalized linear mixed model (GLMM) with a Poisson distribution using a log link function will be used.

Primary Predictor: Day (representing days 1 through 28 of EMA collected responses). Random Effect: Participant ID (id).

5. Hypothesis Testing:

Null Hypothesis: There is no effect of day on the outcome measure. Alternative Hypothesis: There is a significant effect of day on the outcome measure. The significance level will be set at $\alpha = 0.05$. Any p-value below this threshold will lead to rejection of the null hypothesis in favor of the alternative.

6. Assumptions and Limitations:

The models for a23 and a22 assume a binomial distribution of the outcome. The model for a15 assumes a Poisson distribution of the outcome.

7. Reporting:

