Interpretation of the results will focus on the effect of day on the outcome measures. A significant effect would imply that the respective behavior changes across the time period observed.

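### With only a participant random effect and a fixed Poisson variance, the Day test for cigarettes (a15) rejects well above 5% if smokers' trends differ or counts are overdispersed

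*SAP*

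**What the plan says.** SAP section 4 sets a logistic mixed model for loss of control (a23) and overeating (a22), and a log-link Poisson mixed model for cigarettes since the previous prompt (a15). Each has the same structure: "Primary Predictor: Day (representing days 1 through 28 of EMA collected responses). Random Effect: Participant ID (id". Section 5 tests Day at 0.05. Section 6 states "The model for a15 assumes a Poisson distribution of the outcome" and gives no check or alternative. Section 7 then reads the test this way: "A significant effect would imply that the respective behavior changes across the time period observed".

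The protocol has no analysis section that adds to this. It plans the numbers (section 8a): "Sample will consist of 50 smokers and 50 individuals who binge eat (BED". It also sets the measurement schedule (section 2, Mobile Interaction Period): "We will prompt them four times daily to inquire about health risk behavior", for 28 days.

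**The concern.** A random intercept lets participants differ in level, not in trend. If trends do differ, the average Day effect varies from sample to sample by more than the model's standard error allows. Extra-Poisson variation in a15 has the same effect.

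The protocol gives reasons to expect both departures among smokers:

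- **Differing trends.** The app is described as "a science-based behavior change intervention delivered via an interactive, self-directed mobile platform". The aim is cessation: "Smoking participants will have a goal of smoking abstinence by the end of the study". Pharmacological help is optional: "Participants in the smoking sample may use nicotine replacement medications, and we will track which participants use these medications". One common slope would require those who quit and those who do not to follow the same trend.
- **Overdispersion.** a15 counts cigarettes since the previous prompt, and prompts fall at random within windows, at least one hour apart. With the protocol's example windows, the gap between successive prompts on the same day can run from 1 hour to 7 hours (8 AM to 3 PM). The model has no term for that length.

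a15 is the SAP's only smoking outcome, so its smoking conclusion rests on this one test. A standard error that is too small can turn chance variation between smokers into a reported change in behaviour.

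**Working it through.** **Inputs from the documents.** α = 0.05, taken as two-sided; 50 people per model; 4 × 28 = 112 prompts per person; at least 5 cigarettes a day at entry (protocol section 8h), so 5/4 = 1.25 per prompt. A mean of 2.5 (10 a day) is used as a second value.

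**Assumptions, because the documents give no figure.** 80% of prompts answered; numeric Day, scaled so that its coefficient is the day 1–28 change on the link scale; average Day effect zero; intercept SD 0.5 or 0.8 for counts and 1.0 for logits; 25% prevalence for the yes/no items. Let s be the between-person SD of the day 1–28 change. For a15, s = 0.1, 0.25 and 0.5 put about two thirds of smokers within −10/+11%, −22/+28% and −39/+65% of the average trend.

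**Scale of s.** If 5 of 50 smokers went from 5 to 1 a day and the rest did not change, s = ln 5 × √(0.1 × 0.9) = 0.48. This shows only how large s can be. The average log change there is −0.1 × ln 5 = −0.16, so it is not a zero-effect case.

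**Closed form.** The variance of scaled Day is (28² − 1)/(12 × 27²) = 0.0895. Per-person information on the slope is I = 112 × 0.8 × 0.0895 × mean = 8.02 × mean. The true variance of the Day estimate exceeds the model's by a factor φ + s²I, where φ is variance/mean of the counts, so

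rejection = 2 × [1 − Φ(1.96/√(φ + s²I))].

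- Mean 1.25 (I = 10.0): s = 0.25 gives √(1 + 0.627) = 1.28 and 12.4%; s = 0.5 gives √(1 + 2.51) = 1.87 and 29.5%.
- Mean 2.5 (I = 20.0): 19.2% and 42.4%.
- Negative binomial, s = 0, φ = 1 + 1.25/k: k = 5, 2, 1 give φ = 1.25, 1.625, 2.25 and 8.0%, 12.4%, 19.1%.
- Yes/no items at 25% (I = 8.02 × 0.25 × 0.75 = 1.50): s = 0.25, 0.5, 1.0 give 6.1%, 9.5%, 21.5%.

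**Simulation of the SAP model** (Laplace fit, 1,500 runs per scenario; Monte Carlo SE 0.6 points at 5%, 1.3 at 50%):

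| Zero-average scenario | Rejection |
|---|---|
| a15, SAP assumptions true | 4.3% |
| a15, s = 0.1 | 5.3–9.7% |
| a15, s = 0.25 | 13.3–25.5% |
| a15, s = 0.5 | 32.6–52.1% |
| a15, s = 0.25 / 0.5, 70% response, mean 1.25 | 12.5% / 30.4% |
| a15, negative binomial k = 5 / 2 / 1, s = 0, mean 1.25 | 8.5% / 13.6% / 21.0% |
| a15, underdispersed (variance/mean 0.58), s = 0 | 1.2% |
| Yes/no items, s = 0 / 0.25 / 0.5 / 1.0 | 4.7 / 5.7 / 9.3 / 21.4% |

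The first row reproduces the nominal 5% when the SAP's assumptions are true. Simulated a15 rates exceed the closed form, which treats all smokers as equally informative; in the fitted model heavier smokers carry more weight.

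A second simulation, at 5 and 10 cigarettes a day and 30% prevalence, agrees: a15 4.4–5.0% with the SAP model true, 16–24% at s = 0.25, 39–50% at s = 0.5, and 17–24% with k = 2; yes/no items 5.8%, 8.5% and 23.7% at s = 0.25, 0.5 and 1.0.

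**Same data, repaired test.**

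- Participant-clustered standard error, t on 49 df: 4.5–6.9% in all 18 zero-effect count scenarios and 4.2–5.3% in all 4 yes/no scenarios. In the second simulation it reached 7.7% for a15, so it is slightly liberal.
- Random intercept plus Day slope (400 runs): 2.8–7.2% for counts, including overdispersed ones, and 4.0–5.5% for yes/no items.
- Negative binomial with Day slope (200–250 runs): 1.6% at k = 2, s = 0, and 6.5% at k = 2, s = 0.25.

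**The case against.** The omission itself is not in dispute. The case against giving it much weight has five parts.

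- **The size is assumed.** The documents give neither slope SD nor dispersion. This stands, and it is why ranges are shown. Underdispersion pulls the other way: with variance/mean 0.60 and mean 1.25, rejection is 2.0% at s = 0.1 and 8.8% at s = 0.25. It is still 33% at s = 0.5.
- **Zero average with wide spread may be unlikely.** These smokers want to quit, so differences may be mostly falls, and a rejection would then be correct. The documents neither show nor exclude increases that offset them. A nominal 5% test must hold its level when the average is zero, and this one does so only if s is near zero and counts are not overdispersed.
- **The null is unsettled.** Section 5 does not say whether it means no average trend or no trend in anyone. The average is the natural reading of a fixed effect, and all rates above use it. The SAP should say so.
- **The repair lowers rejection of real declines when trends differ.** In the 5-of-50 case it falls from 43% to 20% (mean 1.25) and from 66% to 20% (mean 2.5). This is a real consequence and should be stated. Much of the higher figure comes from the invalid standard error, so it is not all lost power.
- **a23 and a22 are little affected.** This stands: a yes/no answer carries less information per prompt.

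**Conclusion.** The concern holds, and for a15 it should be fixed before the result is relied on. The SAP's a15 test keeps its level if all smokers share one trend and counts are Poisson. At zero average change it rejects in roughly 13–26% of trials at s = 0.25 and 33–52% at s = 0.5, and in 8.5–21.0% with overdispersion alone. Nothing in the plan would detect or handle either departure. For a23 and a22 the rate stays below 10% up to s = 0.5 and reaches 21.4% only at s = 1.0, so the change there is a safeguard.

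These figures rest on 50 people, 70–80% response, numeric Day (the SAP does not say), the average-effect null, and reading the participant term as an intercept. If a Day slope was intended, the SAP needs to state it.

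**What to change.** - **SAP section 4, all three models:** add that Day is tested with a participant-clustered (sandwich) standard error and a t reference on (participants − 1) degrees of freedom. If the software cannot do this, use a correlated random intercept and random Day slope by participant. Name one as the decision rule in advance and report the other as sensitivity.
- **a15 only:** also fit a negative binomial mixed model with random intercept and Day slope, and report its dispersion and Day estimate beside the Poisson result. It should not be the decision rule, given its 1.6% rejection at k = 2, s = 0.
- **SAP section 5:** state that the null is a zero population-average Day effect, and whether Day is numeric.

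The cost is SAP wording and a few lines of code, with no new data. If the Poisson assumptions hold, power for a Day effect of −0.125 (a 12% fall over 28 days) goes from 80.3% to 79.1%. If trends differ, the test will reject real average declines less often than the SAP model does. Random-slope and negative binomial fits may need some convergence work. The SAP is dated August 2023, after the protocol's planned end of August 2022; if the models have already been run, report the change as a labelled re-analysis.
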